6.2.3. Laboratory Abnormalities

Laboratory abnormalities as characterized by type, frequency, severity (as graded by NCI CTCAE v. 4.03) and timing. Abnormalities occurring during the 7 day lead in phase for PK will be summarized separately from abnormalities occurring after first dose of MK-3475 (C1D1).

For summaries of the lead-in PK phase and the treatment period starting at C1D1, baseline will be defined as the last evaluation within 28 days prior to the first dose of axitinib and MK-3475, respectively. For laboratory summaries of the entire treatment period (including by cycle), baseline will be defined as the last evaluation within 28 days prior to the first dose of either axitinib or MK-3475, whichever occurs first.

6.3. PK Endpoints

Axitinib pharmacokinetic analysis will be conducted at Pfizer. The MK-3475 pharmacokinetic analysis will be conducted at Merck and results will be shared with Pfizer.

Pharmacokinetic parameters for axitinib:

- C_{max} , T_{max} , AUC_{0-12} , CL/F and V_z/F as data permit.

6.4. Biomarker Endpoints

Translational and pharmacodynamic biomarkers will be assessed separately for blood and tumor biopsy specimens. These will include measurements of DNA, RNA or protein markers known or suspected to be of relevance to the mechanism of action, the development of resistance, or the identification of those patients who might benefit from treatment with axitinib and MK-3475 combination. The assessment will include pre- and post-baseline blood level of circulating biomarkers; Circulating markers that may be analyzed include, but may not be limited to soluble proteins/cytokines such as VEGF-A, VEGFR2, IL8 and T-cell receptor expansion.

Archival tumor biospecimens (all patients) and baseline *de novo* biospecimens from metastatic lesions (expansion cohort) will be assessed. Post-baseline assessment may be performed for expansion cohort. Tumor biopsies assessment will include tumor tissue biomarkers (e.g, drug targets such as PD-L1; and other markers, such as CD68).

6.5. Covariates

None.

7. HANDLING OF MISSING VALUES

7.1. Missing Dates

In compliance with Pfizer standards, if the day of the month is missing for any date used in a calculation, the 1st of the month will be used to replace the missing date unless the calculation results in a negative time duration (e.g., date of resolution cannot be prior to date of onset; if replacing resolution date with the 1st of the month results in a negative duration, the resolution date will be set to the onset date.). In this case, the date resulting in 0 time duration will be used. Pfizer standards are also used if both month and day are missing (Jan 1 unless negative time duration). For PFS, TTR, DR and OS, if conventions result in a negative duration, durations will be reset to 1 day.

If the start date is missing for an AE, the AE is considered to be treatment emergent unless the collection date is prior to the treatment start date.

7.2. Missing Efficacy Endpoint Values

For all efficacy analyses no values will be imputed for missing data, except as specified in Section 6.1, where for ORR, patients with no post-baseline tumor evaluations will be counted as non-responders.

7.3. Pharmacokinetics

Concentrations below the limit of quantification:

In all data presentations (except listings), axitinib concentrations below the limit of quantification (BLQ) will be set to zero. In listings, BLQ values will be reported as “<LLQ”, where LLQ will be replaced with the value for the lower limit of quantification for axitinib.

Deviations, missing concentrations and anomalous values:

For summary tables and plots of median profiles, appropriate summary statistics will be calculated. Concentrations will be set to missing if one of the following cases is true:

1. A concentration has been reported as ND (i.e., not done) or NS (i.e., no sample),
2. A deviation in sampling time is of sufficient concern or a concentration has been flagged as anomalous by the pharmacokineticist.

Note that summary statistics will not be presented at a particular time point if more than 50% of the data are missing. For analysis of PK concentrations, no values will be imputed for missing data.

Pharmacokinetic parameters:

Axitinib pharmacokinetic analysis will be conducted at Pfizer. The MK-3475 pharmacokinetic analysis will be conducted at Merck and results will be shared with Pfizer.

Actual PK sampling times (and where possible the actual dosing information) will be used in the derivation of axitinib PK parameters. If a PK parameter cannot be estimated from a subject's concentration data, the parameter will be coded as NC (i.e., not calculated). (Note that NC values will not be generated beyond the day that a subject discontinues).

In summary tables, statistics will be calculated by setting NC values to missing; and statistics will not be presented for a particular treatment if more than 50% of the data are NC. For statistical analyses (i.e., analysis of variance), PK parameters coded as NC will also be set to missing.

If an individual subject has a known biased estimate of a PK parameter (due for example to an unexpected event such as vomiting before all of the drug is absorbed in the body), this will be footnoted in summary tables and will not be included in the calculation of summary statistics or statistical analyses.

For PK analysis, patients will be required to have at least one quantifiable concentration of each drug to be included in the concentration summary. For evaluation of changes in PK of axitinib when administered alone vs in combination, only patients with matching pair of PK assessments under both conditions will be included in the PK summary. Patients who have been treated with axitinib for whom drug plasma concentrations (from both PK visits, when administered alone and in combination) are available will be included in average concentration summary.

7.4. Pharmacodynamic Biomarkers

For analysis of pharmacodynamic biomarkers, no values will be imputed for missing data.

Duplicate biomarker (i.e., more than one set of data for a particular visit) is not expected. For continuous data, if duplicate data is received, the results will be averaged and the average value will be used. The average value will be added to the analysis dataset. For non-continuous data, the results will be reviewed by the study team and a representative sample will be selected. The representative sample will be flagged in the analysis dataset.

8. STATISTICAL METHODOLOGY AND STATISTICAL ANALYSES

8.1. Statistical Methods

8.1.1. Statistical Methods for Dose Escalation: Up-and-Down Matrix Design with the mTPI Method

The mTPI design uses a Bayesian statistics framework and a beta/binomial hierarchical model to compute the posterior probability of three dosing intervals that reflect the relative difference between the toxicity rate of each dose level to the target rate ($pT = 0.30$). If the toxicity rate of the currently used dose level is far smaller than pT , the mTPI will recommend escalating the dose level; if it is close to pT , the mTPI will recommend continuing at the current dose; if it is far greater than pT , the mTPI will recommend de-escalating the dose level. These rules are conceptually similar to those used by the 3+3 design, except the decisions of an mTPI design are based on posterior probabilities calculated under a coherent probability model.

Being a model-based design, mTPI automatically and appropriately tailors dose-escalation and de-escalation decisions for different trials with different toxicity parameters. More importantly, all the dose-escalation decisions for a given trial can be pre-calculated under the mTPI design and presented in a two-way table ([Appendix 4](#)). Thus, compared to other advanced model-based designs published in the literature, the mTPI design is logically less complicated and easier to implement. Recently, a Phase 1 trial based on the mTPI design has been published.⁴

Decision rules are based on calculating unit probability mass (UPM) of three dosing intervals corresponding to under, proper, and over dosing in terms of toxicity. Specifically, the underdosing interval is defined as $(0; pT - e_1)$, the over-dosing interval $(pT + e_2)$, and the proper-dosing interval $(pT - e_1, pT + e_2)$, where e_1 and e_2 are small fractions. Based on the safety profile of axitinib and MK-3475, e_1 is selected as 0.05, and e_2 is selected as 0.03. Therefore, the target dosing interval for the DLT rate is $(0.25, 0.33)$.

The three dosing intervals are associated with three different dose-escalation decisions. The under-dosing interval corresponds to a dose escalation (E), over-dosing corresponds to a dose de-escalation (D), and proper-dosing corresponds to remaining at the current dose (R). Given a dosing interval and a probability distribution, the unit probability mass (UPM) of that dosing interval is defined as the probability of a subject belonging to that dosing interval divided by the length of the dosing interval. The mTPI design calculates the UPMs for the

three dosing intervals, and the one with the largest UPM informs the corresponding dose-finding decision, which is the dose level to be used for future patients. For example, if the under-dosing interval has the largest UPM, the decision will be to escalate, and the next cohort of patients will be treated at the next higher dose level. Ji and collaborators have demonstrated that the decision based on UPM is optimal in that it minimizes a posterior expected loss (ie, minimizes the chance of making a wrong dosing decision)⁵.

The dose-finding component of the trial is completed when at least 10 evaluable patients have been treated at the highest dose with DLT rate < 0.33. It is estimated that approximately 20 DLT evaluable patients have been enrolled to reach 10-DLT evaluable patients at the estimated MTD.

8.1.2. Methods for Estimating the MTD

The estimated MTD will be the highest tested dose level with a DLT rate < 0.33 in 10 DLT evaluable patients. We assume that higher doses of MK-3475 result in higher toxicity rates. But, due to the relatively low number of patients that may be potentially allocated to any dose combination, this assumption may be violated. For example, at the end of the study, the dose combination (MK-3475 2 mg /kg q3wks, axitinib 5 mg BID) may have a higher proportion of observed toxicities than, say, (MK-3475 1 mg /kg q3wks, axitinib 5 mg BID), and this variability may be simply related to small cohort size alone. To overcome this potential problem, we use a bivariate isotonic regression to smooth the resulting toxicity surface to a monotonically increasing one. The determination of the MTD contour is accomplished using the Dykstra-Roberston algorithm.⁶ Once a monotonically increasing toxicity surface is obtained (either observed or smoothed according to the bivariate isotonic regression algorithm), the MTD combinations closest to the targeted DLT rate of 0.3 but still < 0.33 are calculated.

8.1.3. Sample Size Determination

The sample sizes planned for the study arise from logistic feasibility and past experience with Phase 1b studies in oncology and are not entirely driven by statistical considerations. It is expected that approximately 60 patients will be required to achieve all study objectives.

Due to the dynamic nature of the Bayesian allocation procedure, the sample size of the Up-and-Down design using the mTPI approach cannot be determined in advance. It is estimated 20 DLT evaluable patients will be enrolled in the dose finding stage in order to have a reliable and accurate estimate of the MTD. In addition, there will be a Dose Expansion Phase cohort to characterize safety, biomarkers, and efficacy in terms of probability (p) of achieving an event of interest including, but not limited to, objective response (OR). The goal will be to estimate proportions of such patients with the standard error (SE) of not greater than 0.08, ie, by definition,

$$SE = \sqrt{\frac{p(1-p)}{n}} \leq \frac{1}{2\sqrt{n}}$$

Therefore, a sample of forty patients ($n=40$) in the Dose Expansion Phase cohort will allow estimation of the probability of achieving an event of interest with the standard error ≤ 0.08 .

The sample size estimate for the expansion cohort also takes into consideration the key tumor biomarker PD-L1 endpoints. If the observed rate of PD-L1 positives is 20% then approximately 40 patients would be required to enroll 8 PD-L1 positive patients.

8.2. Statistical Methods for Different Types of Endpoints

Listings and standard summary statistics will be used to analyze the study.

Analysis of Time-to-Event Endpoints

Time-to-event endpoints will be summarized using the Kaplan-Meier method and displayed graphically when appropriate. Medians and two-sided 95% confidence intervals will be provided.

Analysis of Binary Endpoints

Binary endpoints will be summarized by percentage rates along with the 95% confidence intervals using an exact method.

Analysis of Continuous Endpoints

Continuous endpoints will be summarized by descriptive statistics, including the mean, standard deviation, median, minimum, and maximum values.

Analysis of Categorical Endpoints

The number and percentage of patients in each category will be provided for categorical variable.

8.3. Statistical Analyses

8.3.1. Standard Analyses

- **Study Conduct and Patient Disposition** - an accounting of the study patients in the safety analysis (SA) population will be provided. Patients not meeting the eligibility criteria will be listed. Patients not completing the study will be listed along with the reason for their discontinuation. Reasons for discontinuation will be summarized.
- **Baseline Characteristics** – for patients in the SA population, characteristics such as age, height, weight, race, ethnicity, diagnosis, performance status, MSKCC risk group and medical history at study entry will be summarized in frequency tables, and descriptive statistics will be provided for quantitative variables.
- **Treatment Administration/Compliance** – Administration of study medication will be presented for the SA population, by medication administered within each treatment group and will be described in terms of the duration of treatment in days (mean, median and range), number of cycles administered (mean, median and range), dose intensity,

dose modifications, dose interruptions, dose delays. Summaries for axitinib will include drug that may have been received during the lead-in PK period.

8.3.2. Analysis of Efficacy Endpoints

PFS, DR, and OS will be summarized using the Kaplan-Meier method and displayed graphically. The median event time and 2-sided 95% confidence interval (CI), calculated using the Brookmeyer-Crowley method, for the median will be provided for each endpoint.

Six-month and twelve-month progression-free survival (6m-PFS and 12m-PFS) will be summarized as a product limit estimator based on the Kaplan-Meier method to account for censored events, together with the corresponding 2-sided 95% CI. The 2-sided 95% CI for the $\log[-\log(6 \text{ and } 12\text{-month PFS probabilities})]$ will be calculated using normal approximation and then back transformed to give the CI for the 6 and 12-month PFS rates. Analysis results will be included in the table for the PFS analysis.

The ORR will be summarized along with the corresponding exact 2-sided 95% CI calculated using a method based on the F distribution. If a patient has not achieved an objective response, but remain stable for at least 12 weeks, then the best overall response for such a patient will be SD.

For TTR, descriptive statistics including the mean (95% CI), median, and range will be provided.

Tumor Response will be presented in the form of patient data listings that include, but are not limited to, lesion type (target/non-target), received (maximum) dose, overall tumor response at each visit, and best overall response. In addition, progression date, death date, date of first response and last tumor assessment date, dates of first dose and last dose will be listed, together with DR, PFS and OS.

Listings or/and tables (when applicable) will be sorted by treatment cohort.

Analysis Sets

- Response-evaluable population for Tumor Response, PFS and OS (dose expansion cohort including the patients from the Dose Escalation Phase of the study treated at the MTD).
- Patients with an overall objective response of CR or PR in the response-evaluable population for Duration of Tumor Response and Time to Response (dose expansion cohort including the patients from the Dose Escalation Phase of the study treated at the MTD).

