## SCHEDULE OF ACTIVITIES

Protocol Activities 	Screening	Lead-in PK Period 		Study Treatment (1 cycle = 21 days)			Post-Treatment	
				Cycle 1	Cycles ≥2			
	≤28 Days Prior to Registration	Day 1 (±2 days)	Day 7	Day 1 (±3 days)	Day 5 (±2 days)	Day 1 (±3 days)	End of Treatment /Withdrawal (±3 days) 	Follow-up Day 28 (+7 days) After Last Dose 
Documentation								
Informed Consent 	X							
Medical/Oncological History 	X							
Baseline Signs/Symptoms 		X		(X)				
Physical Examination 	X			X		X	X	
ECOG Performance Status	X	X		X		X	X	
In Clinic Blood Pressure, Pulse Rate 	X	X	X	X		X	X	
Home Blood Pressure Monitoring 	X				X			
Follow-up for Axitinib Dosing Compliance 					X	As needed based on axitinib dose modifications		
Laboratory Studies								
Hematology 	X	(X)		X		X	X	
Blood Chemistry 	X	(X)		X		X	X	
Coagulation 	X	(X)		X		X	X	
Urinalysis 	X	(X)		X		X	X	
12-lead ECG 	X			X			X	
Thyroid Function Tests 	X	(X)		X		X		
Pregnancy Test 	X	X		X		X	X	
Disease Assessments								

Protocol Activities 	Screening	Lead-in PK Period 		Study Treatment (1 cycle = 21 days)			Post-Treatment	
		Cycle 1			Cycles ≥2			
	≤28 Days Prior to Registration	Day 1 (±2 days)	Day 7	Day 1 (±3 days)	Day 5 (±2 days)	Day 1 (±3 days)	End of Treatment /Withdrawal (±3 days) 	Follow-up Day 28 (+7 days) After Last Dose 
Tumor Assessments (including scans) 	X					X (at 12 weeks and then every 6 weeks)	X	
Other Clinical Assessments								
Adverse Events 		X						
Survival 								X
Concomitant Medications/Treatments 	X	(X)	X	X		X	X	X
Registration and Study Treatment 								
MK-3475 				X 		X 		
Axitinib 		X						
Other Samplings								
Pharmacokinetics 			X	X	X	X (Cycles 3, 5, 7, 11 and then q12w)		
Serum Biomarkers 	X					X (Cycle 2 only)	X	
Whole Blood Biomarkers 	X					X (Cycle 2 only)	X	
Banked Biospecimen 	X							
Archival Tumor Tissue 	X							
De Novo Tumor Biospecimen 	X					X 		
Anti-MK-3475 Antibodies 				X		X 		X 

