Footnotes for Schedule of Activities
1. Protocol Activities: All assessments should be performed prior to dosing with study medications unless otherwise indicated. Acceptable time windows for performing each assessment are described in the column headings.
2. Lead-in PK Period: All patients in the Dose Finding Phase, and at least 8 patients in the Dose Expansion Phase.
3. End of Treatment/Withdrawal: Obtain these assessments if not completed in the prior week, except for tumor assessment which need not be repeated if performed within the prior 6 weeks.
4. Follow-up Day 28 after last dose: To occur at least 28 days, and no more than 35 days, after discontinuation of treatment. See footnote 19 and Section 8.1.1 .
5. Informed Consent: Must be obtained prior to undergoing any trial specific procedure.
6. Medical/Oncological History: To include information on prior systemic adjuvant or neoadjuvant therapy regimens, surgery and radiation therapy.
7. Baseline Signs/Symptoms: To be documented and recorded at Lead-in Day 1 or Cycle 1 Day 1 predose for all patients.
8. Physical Examination: Includes an examination of major body systems, assessment of ECOG performance status, and weight (height included at screening only).
9. In Clinic Blood pressure, pulse rate: Blood pressure, and pulse rate should be taken with the patient in the seated position after the patient has been sitting quietly for at least 5 minutes. Two blood pressure readings will be taken at least 1 hour apart at each clinic visit.
10. Home blood pressure monitoring: All patients will receive home blood pressure monitoring devices and blood pressure will be monitored at home. While on axitinib (as single agent during the Lead-in, or combined with MK-3475) patients will monitor their blood pressure at least twice daily (before taking each dose of axitinib) and blood pressure should be recorded in a patient diary. Patients should be instructed to contact the site immediately for guidance if their systolic blood pressure rises above 150 mm Hg, diastolic blood pressure rises above 100 mm Hg, or if they develop symptoms perceived to be related to elevated blood pressure (eg, headache, visual disturbance) although a different blood pressure threshold for contacting the site may be used according to the Investigator's clinical judgment (see Section 5.2.7.3 ).

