19. **Adverse Events:** Adverse events should be documented and recorded at each visit using NCI CTCAE version 4.03. For SAEs, the active reporting period to Pfizer or its designated representative begins from the time that the patient provides informed consent, which is obtained prior to the patient's participation in the study, ie, prior to undergoing any study-related procedure and/or receiving investigational product, through and including 90 calendar days after the last administration of the investigational product and before initiation of a new anti-cancer treatment. The prolonged follow up is due to the pharmacokinetic properties of the investigational product MK-3475. SAEs experienced by a patient after the active reporting period (see [Section 8.1.1](#)) has ended should be reported to the Sponsor if the Investigator becomes aware of them; at a minimum, all SAEs that the Investigator believes have at least a reasonable possibility of being related to study drug are to be reported to the Sponsor. AEs (serious and non serious) should be recorded on the Case Report Form (CRF) from the time the patient has taken at least one dose of study treatment through last patient visit (Day 28 after last dose). If a patient begins a new anticancer therapy, the AE reporting period for non serious AEs ends at the time the new treatment is started. Pregnancy or breast feeding that occur during the trial, within 120 days of discontinuing treatment with MK-3475, or within 28 days after the cessation of study treatment if the patient begins a new anticancer therapy, whichever is earlier, should be reported as in [Section 8.4 \(Exposure During Pregnancy\)](#).

20. **Concomitant Medications/Treatments:** Concomitant medications and treatments will be recorded from 28 days prior to the start of study treatment and up to 28 days after the last dose of study treatment. All concomitant medications should be recorded in the CRF including supportive care drugs (eg, anti-emetic treatment and prophylaxis), and the drugs used to treat adverse events or chronic diseases, and non-drug supportive interventions (eg, transfusions).

21. **Registration:** Patient number and dose level allocation operated by Pfizer Inc. Required information: site and patient identifiers and demographic information. Study treatment (either single agent axitinib for patients in Lead-in or axitinib in combination with MK-3475 for all other patients) should begin within 7 days of registration.

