#### **6.1.1. Tumor Biospecimens**

Provision of archival tumor biospecimens (all patients) and baseline *de novo* biospecimens from metastatic lesions (expansion cohort) is mandatory for all patients. Although baseline *de novo* biopsies taken from metastatic lesions prior to the date of screening are acceptable, sponsor provided neutral buffered formalin in kits for preferred collection on the date of screening to optimize tissue fixation for subsequent analysis. A second *de novo* biopsy is strongly encouraged and collected at the time of first tumor assessment at after 4 Cycles of treatment (12 weeks). It is recommended, if possible, that the 12 week biopsy be taken from a lesion in the same anatomical location and also fixed in sponsor provided neutral buffered formalin.

For archival tumor biospecimens, formalin fixed, paraffin embedded (FFPE) tissue block(s) from initial diagnosis that contain sufficient tissue to generate at least 12 slides, each with tissue sections (4 microns thickness preferred, 5 microns thick acceptable), will be collected. If no FFPE block is available, then at least 12 unbaked and unstained slides containing FFPE tissue sections, 5 microns thick acceptable). However FFPE blocks are strongly encouraged over slides. See [Section 7.3.1](#). Additional information on tumor biospecimen collection, processing and immediate shipping procedures is included in the study laboratory manual.

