The cytological confirmation of the neoplastic origin of any effusion that appears or worsens during treatment when the measurable tumor has met criteria for response or stable disease is mandatory to differentiate between response or stable disease and progressive disease.

Confirmation of Tumor Response

To be assigned a status of PR or CR, changes in tumor measurements in patients with responding tumors must be confirmed by repeat studies that should be performed ≥ 4 weeks after the criteria for response are first met. In the case of SD, follow-up measurements must have met the SD criteria at least once after study entry at a minimum interval of 12 weeks.

Determination of Tumor Response by the RECIST Criteria

When both target and non-target lesions are present, individual assessments will be recorded separately. Determination of tumor response at each assessment is summarized in the following table.

Response Evaluation Criteria in Solid Tumors

Target Lesions ¹	Non-Target Lesions ²	New Lesions ³	Tumor Response
CR	CR	No	CR
CR	Non-CR/non-PD	No	PR
CR	Not evaluated	No	PR
PR	Non-PD or not all evaluated	No	PR
SD	Non-PD or not all evaluated	No	SD
PD	Any response	Yes or No	PD
Any response	PD	Yes or No	PD
Any response	Any response	Yes	PD

¹ Measurable lesions only.

² May include measurable lesions not followed as target lesions or non-measurable lesions.

³ Measurable or non-measurable lesions

Determination of Best Overall Response

The best overall response is the best response recorded from the start of the treatment until disease progression/recurrence (taking as reference for progressive disease the smallest measurements recorded since the treatment started). For CR and PR, the patient's best response assignment will depend on the achievement of both measurement and confirmation criteria. In the case of SD, follow-up measurements must have met the SD criteria at least once after study entry at a minimum interval of 12 weeks.

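### The stable-disease minimum equals the nominal first-scan time with no tolerance and no defined start, so for a few patients best overall response can turn on a scan done 1 to 3 days early

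*SAP*

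**What the plan says.** SAP 8.3.2 assigns SD as best overall response to a patient without an objective response who "remain stable for at least 12 weeks". It gives no start date for that interval.

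SAP Appendix 3 states the rule twice, under confirmation of response and under determination of best overall response: "follow-up measurements must have met the SD criteria at least once after study entry at a minimum interval of 12 weeks". Protocol Appendix 2 carries the same wording in the same two places. Neither document defines study entry, and neither names a category for a patient who is stable for less than 12 weeks.

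In the protocol Schedule of Activities, the on-treatment tumor assessment is marked "X (at 12 weeks and then every 6 weeks" in a column whose heading allows ±3 days around Day 1 of the cycle. Footnote 1 says: "Acceptable time windows for performing each assessment are described in the column headings". The same table fixes "1 cycle = 21 days", and protocol 6.1.1 places the first tumor assessment after four cycles.

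SAP 6.1 starts PFS, TTR and OS at the first MK-3475 dose (C1D1), and SAP Appendix 2 starts the on-study efficacy period there too.

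**The concern.** The SD threshold sits in the middle of the permitted window for the first scan. A site can follow the protocol exactly and still produce a first scan that falls short of the minimum. Two patients with the same course, both stable at the first scan and both progressing by the second, could then receive different best overall responses because of the appointment date alone.

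At stake is how cleanly the SD category can be read. Best overall response is a planned listing for the expansion cohort (SAP 8.3.2, protocol 9.4.1), and it is the only efficacy output that protocol 9.4 plans for the Dose Finding cohorts. Any tabulation under the general rule for categorical endpoints in SAP 8.2 would inherit the problem. ORR, DR, TTR, PFS and OS do not use the SD category and do not change.

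**Working it through.** **Nominal time.** Four cycles × 21 days = 84 days, and 12 weeks × 7 = 84 days. The plan's own equivalence of four cycles and 12 weeks reproduces, and it equals the SD minimum exactly.

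**Permitted scan days.** 84 − 3 = 81 to 84 + 3 = 87 days after C1D1.

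**Comparison with an 84-day minimum, by start of the clock:**

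| Start of the SD interval | In-window first scan falls at | Window days that miss 84 |
|---|---|---|
| C1D1, elapsed days | 81–87 | 3 of 7 (81, 82, 83) |
| C1D1, with the +1 day used in the SAP 6.1 duration formulas | counted as 82–88 | 2 of 7 |
| Registration 3 days before C1D1 | 84–90 | 0 of 7 |
| Registration 7 days before C1D1 | 88–94 | 0 of 7 |
| Lead-in Day 1, 7 days before C1D1 | 88–94 | 0 of 7 |

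The registration rows rest on Schedule of Activities footnote 21, under which treatment "should begin within 7 days of registration".

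**Second scan.** 18 weeks = 126 days, so the earliest in-window second scan is at 126 − 3 = 123 days. A patient still stable then meets the minimum under every clock. The affected group is therefore narrow: an early first scan, SD at that scan, and no later stable scan (progression, death, dropout or other therapy first).

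**Size, as an illustration.** Expected number = patients × share of first scans done early × share with SD at the first scan only. The documents give neither share. I assume 1/7 to 3/7 for the first and 5% to 20% for the second.

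- Expansion patients without a lead-in: 40 − 8 = 32 (8 is the stated minimum with a lead-in).
  - Low: 32 × 1/7 × 0.05 = 0.23
  - High: 32 × 3/7 × 0.20 = 2.74
- If C1D1 is the clock for everyone, lead-in patients are exposed too. With 10 Dose Finding patients at the MTD pooled in, as SAP 8.3.2 provides, the base is 40 + 10 = 50.
  - Low: 50 × 1/7 × 0.05 = 0.36
  - High: 50 × 3/7 × 0.20 = 4.29

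**After the change.** With a minimum of 81 elapsed days from C1D1, all in-window first scans (81 to 87) qualify, so 0 of 7 window days fail.

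**The case against.** The strongest reply is that the failure needs a clock the documents never set. Appendix 3 counts from study entry. If that means registration 3 or more days before C1D1, or lead-in Day 1, every in-window scan passes. This stands. It limits the problem to a clock starting at C1D1 or within 2 days before it, and it shows that the missing origin is the more basic gap. It does not remove the problem, because C1D1 is the origin the SAP uses for its other efficacy times and so a likely choice in programming.

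A second reply is that the sentence in 8.3.2 does not itself require a scan on or after day 84. A patient stable on day 82 with progression first documented at week 18 could be read as having been stable beyond 12 weeks. That reading is open on 8.3.2 alone. Appendix 3, however, ties SD to a measurement "at least once after study entry at a minimum interval of 12 weeks", so the two SAP passages can give different answers for the same patient.

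Third, the consequence is small. The trial is single-arm and descriptive, there is no disease-control endpoint, the efficacy table in SAP 8.4 does not include best overall response, and the listings show visit-level responses and dates from which a reader could reclassify a borderline case. All of this stands, and it makes the point minor.

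**Conclusion.** The point holds in a limited form. If the SD interval runs from C1D1, the rule in Appendix 3 gives different best overall responses to compliant patients with the same disease course, depending on whether the first scan fell on days 81 to 83 or 84 to 87. Patients still stable at week 18 are not affected. Nor are lead-in patients if the clock starts at lead-in Day 1.

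A reader might infer more than this, and the documents do not support it:

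- That an early compliant scan can never count towards SD. This depends on the undefined start of the interval, and a later stable scan restores SD.
- That the affected patients become PD or not evaluable. The plan assigns no category to shorter stability.
- That a firm percentage is misclassified. Neither the spread of scan days nor the share with SD at the first scan only is in the documents.

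On the assumed ranges, about 0.2 to 2.7 of 32 patients are affected, or 0.4 to 4.3 of 50 if C1D1 applies to all. The timing arithmetic is firm; the counts are only as good as the two assumed shares.

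**What to change.** In SAP 8.3.2 and in both statements in SAP Appendix 3:

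1. Define SD as SD criteria met at least once at 81 days or more (12 weeks minus the 3-day window) after the first dose of MK-3475 (C1D1), counted as scan date minus first-dose date with no added day.
2. Name the best overall response category for stability shorter than that.
3. Note that this departs from protocol Appendix 2. Protocol section 9 lets the SAP modify the protocol's plans, and only major changes to the primary endpoint or its analysis also need a protocol amendment.

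The cost is a few lines of SAP text and an SD minimum that is 3 days shorter. No visit, scan or treatment changes.
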